## 4.3. Recruitment of Participants

**Aim 1:** De-identified data from the Longitudinal (natural history) Study (LS) of the Urea Cycle Disorders (UCD) will be supplemented with data from subjects identified from two sources: the Studies of Pediatric Liver Transplantation (SPLIT) Research Group and the National Urea Cycle Disorders Foundation (NUCDF).

Longitudinal Study participants will not be recruited to participate in this study, but their data used for this analysis, as is permissible per the LS consent form.

By agreement, when this project is implemented, SPLIT will contact its respective transplant centers to describe the study and its eligibility criteria indicating the number and descriptive characteristics of eligibility based on SPLIT anonymized records asking study staff to contact eligible patients and provide general recruitment materials. NUCDF will also distribute recruitment materials and directly enroll eligible participants to the study. In all cases, interested patients will contact one of the study sites to express their interest in participating in the study.

Enrollment in the UCDC LS will be offered to any patient not already enrolled, so that they can take advantage of the rare disease protocol to capture laboratory data, neurocognitive function and quality of life information, using the resources already in place through the UCDC. Participants interested in enrolling in the LS will be put in

touch with the study coordinator and PI at the nearest (or preferred) UCDC site. The PCORI site coordinator will work closely with LS coordinators to ensure that contact with interested participants is not delayed. We anticipate that a large proportion will agree to participate in the PCORI study, which will require only two visits for neuropsychological testing and self-reported quality of life questionnaire.

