#### **4.4. Retention Strategies**

**Aim 1:** Since this component comprises only 2 visits for neuropsychological testing, we expect a high retention rate among highly motivated patients referred from and enrolled by NUCDF. In comparison, we have observed ~90% retention in the LS protocol since enrollment began in 2006; the LS is more demanding with regard to laboratory and neuropsychiatric testing. UCD appears to affect equally all ethnic groups, except African American, who are underrepresented (~3%). We will make every effort to enroll African American patients in this study.

**Aim 2:** As this component consists of 60-90 minute interviews and/or participation in focus groups, after which subjects exit the study, retention is anticipated to be near 100% (barring the rare occasion when a participant may voluntarily terminate the interview and/or participation in the focus group).

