## 6. Statistical Considerations

### 6.1. Sample Sizes

**Aim 1.** Of the 185 projected members of the target population, 92 (49.7%) are expected to have received liver transplants and 93 (50.3%) to remain on conservative management. Based on previously published results and characteristics of the UCD patients currently enrolled in our longitudinal study, we expect these groups to be very comparable with respect to UCD severity. As described below, we will use the method of covariate-balanced propensity score matching to create additional groups that are more closely matched on additional severity indicators for the comparative effectiveness analysis. **Table 2** provides a detailed breakdown of the characteristics of study groups.

For **Aims 2 and 3**, we plan to recruit a representative sample of 32-48 patient primary caretakers for participation in semi-structured interviews on their experience making treatment decisions for their child with UCD and an additional 16-48 patient primary caretakers (until a sample of 64-80 is reached) for participation in focus groups to validate information obtained through interviews and to discuss effective dissemination strategies for the evidence-based information obtained through this study.

Table 2. Characteristics of Eligible Transplanted Cases and Comparable Controls										
Group	Total	Type of UCD				Sex M/F	Onset (days)	Peak NH3 (µmol/l)		Surgery Age (mo.)
		CPSD	OTCD	ASD	ALD			# >200, %	Median, IQR	
Transplanted	92	12 (14%)	44 (47%)	22 (24%)	14 (15%)	62/30	2 (1-21)	90 (98%)	958, 938	11.7 (1.5-186)
Conservatively Managed	93	1 (1%)	21 (22%)	37 (39%)	34 (38%)	48/45	3. (1-21)	69 (74%)	403, 781	---

Interview and focus group participants will be stratified by their child's: 1) access to expert care (i.e. yes/no), 2) disease severity (i.e. neonatal onset/post-neonatal onset), and 3) transplant status (pre/no transplant, post-transplant,) (**Tables 3 and 4**). Although not included as an explicit level of stratification, we will also aim to recruit primary caretakers that are diverse in terms of their child's geographic distribution, socioeconomic status, and race/ethnicity.

Table 3. Sample Sizes for Stage 1 Patient Caretaker Interviews				
Disease Severity	Pre/No Transplant			
	Access to Expert Care		Sample Size	
	Yes	No		
Neonatal onset		4-6	4-6	8-12
Post-neonatal onset		4-6	4-6	8-12
Post-Transplant				
Neonatal onset		4-6	4-6	8-12
Post-neonatal onset		4-6	4-6	8-12

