## 6.2. Analysis Plan

For **Aim 1**, we will use covariate balancing propensity scoring based on the CBPS package in R [28] to create comparable (balanced) groups based on their risk factor (covariate) profile in subjects according to their propensity (probability) to move from conservative management to liver transplantation. This approach leads to a model that predicts treatment assignment (conservative vs. liver transplantation) and balances covariates, especially those related to study outcome(s), and offers the best opportunity to simulate RCT results from observational data. From prior experience, many through the UCDC [26,31,32], we know many of the important risk factors, which include neonatal vs. late onset, number of prior hyperammonemic events, event severity in terms of hyperammonemic coma score [2], ammonia and glutamine levels at regularly scheduled clinic visits, and duration from birth to transplant or index date. In addition to these, we will consider comorbidities, organ function, and other laboratory assessments. The CBPS software will help us choose the model that maximizes covariate balance and generate the CBPS for each participant. The next steps will be to order the dataset according to the CBPS. It is useful at this point to select CBPS to cut points to form homogeneous strata to assess the number of subjects with a liver transplant and conservative management per stratum. Those strata where there are

insufficient numbers (mismatches) of conservative treatment or liver transplant subjects will be described, documented and excluded from the primary analysis due to lack of covariate balance. Before conducting model-based analyses for **Aim 1**, we will compare survival times based on the log-rank test in Kaplan-Meier analysis and the difference between mean scores based on t-tests by treatment for neurodevelopment and quality of life within each stratum to evaluate evidence of heterogeneity. Evidence of heterogeneity will provide clues to interactive effects based on UCD severity which will be modeled in regression analyses below by including a cross products term of treatment type with CBPS. Based on these results, we will develop general linear random effects longitudinal regression models in STATA 14

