[<http://www.stata.com/stata14/>] to perform analysis of covariance that will enable us to evaluate **Aim 1** outcomes of neurodevelopment and quality of life. Each model will include treatment type, the baseline measurement of each outcome, as well as the CBPS and if necessary the cross product of treatment type by CBPS. When we address survival, we will implement Cox Regression models to predict survival time by treatment and will either control for CBPS or stratify on it in the case of heterogeneity.

We used PASS 12 [33] to evaluate statistical power to address study aims for sample sizes per group (liver transplantation vs. conservative management) of 90 and 80 in 2-tailed testing at an alpha of 0.05, which assumes some losses in the sample entering analysis in order to maintain adequate covariate balance between groups. For neurodevelopmental and quality of life assessments, we have 80% power to detect modest 0.4sd effect size differences between groups assuming two repeated measurements per person correlated at 70% (ICC). For mortality, assuming the rate in the conservatively treated group remains about 28%, the study will have 80% power to detect and increase in the liver transplant group of about 60% which is robust to differences in sample size between 80 and 90 per group. The study is well powered to detect any clinically meaningful difference in neurocognitive outcomes and QOL and adequately powered to detect a moderate difference in mortality between groups.

For **Aim 2**, interview data will be managed using QSR International NVivo 10 software [[http://www.qsrinternational.com/products\\_nvivo.asp](http://www.qsrinternational.com/products_nvivo.asp)], a program that allows us to collect, organize, and code qualitative data sources. Although not explicitly a grounded theory study, our approach to the analysis of primary caretaker and provider interview data will borrow from aspects of Strauss and Corbin's systematic procedures for grounded theory work [34]. No existing framework or theory currently exists that describes the process which UCD patients and their families undertake when making the difficult decision to pursue liver transplant or continue conservative management. Thus, some of Strauss and Corbin's analysis techniques are suitable for this study aim, which seeks to describe a process/experience in a field where there is little pre-existing evidence.

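### The survival analysis sets no time zero, no index-date rule for never-transplanted children, and no rule for pre-transplant time or delayed entry, so it is open to bias of unknown size and direction

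*Combined protocol and SAP*

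**What the plan says.** Section 6.1 defines two groups by the treatment eventually received: "92 (49.7%) are expected to have received liver transplants and 93 (50.3%) to remain on conservative management". Table 2 lists surgery age in the transplanted group as 11.7 (1.5-186) months, without naming the statistic, and shows no corresponding age for the conservative group.

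Section 6.2 is the whole survival plan. The propensity score models "their propensity (probability) to move from conservative management to liver transplantation". One of its covariates is "duration from birth to transplant or index date", the only mention of an index date. Before any modelling, "we will compare survival times based on the log-rank test in Kaplan-Meier analysis", stratum by stratum. Then: "When we address survival, we will implement Cox Regression models to predict survival time by treatment and will either control for CBPS", with stratification as the alternative if effects are heterogeneous.

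On entry, section 4.4 reports that "we have observed ~90% retention in the LS protocol since enrollment began in 2006" (LS is the Longitudinal Study), and the synopsis gives activation as 4 March 2016. Section 4 speaks of merging data from the SPLIT and NUCDF registries. Section 4.3 instead describes recruitment: "In all cases, interested patients will contact one of the study sites to express their interest in participating in the study". Section 5.6, on participants who discontinue, says the study takes an intent-to-treat approach.

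**The concern.** Transplant is something that happens to a child already under conservative management. A child counted as transplanted must have lived to surgery, while a child who dies waiting is counted as conservative. If treatment is a fixed group and the clock starts at birth, that guaranteed survival is credited to transplant (immortal time).

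Entry is the second problem. Children who died before a source could record them are absent. If survivors' earlier time is counted as time at risk, mortality is understated in whichever group enters late (left truncation). Late entry of conservatively managed children makes transplant look worse; recruiting children alive after surgery makes it look better.

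CBPS balances covariates. It does not correct for having survived to transplant or to entry. Survival is one of three Aim 1 outcomes, and families are meant to use it in choosing a treatment.

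**Working it through.** **1. The plan's own figure, as a yardstick.** For mortality, "the study will have 80% power to detect and increase in the liver transplant group of about 60" per cent, from 28%, with 80 to 90 per group. Read as relative, 28% × 1.6 = 44.8%, and the implied hazard ratio (HR) is ln(1 − 0.448)/ln(1 − 0.28) = 1.81. Power = Φ{[0.168√n − 1.96√(2 × 0.364 × 0.636)]/√(0.28 × 0.72 + 0.448 × 0.552)} is 60.0% at n = 80 and 65.1% at n = 90, so the stated 80% is not reproduced. Reaching 80% needs 49.5% (n = 80) or 48.2% (n = 90), an HR of about 2.1 or 2.0. That is a separate matter; 1.81 is used here only for scale.

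**2. What the text fixes.** No section gives a survival origin, a time-dependent treatment term, a landmark or an entry time. The index date cannot be computed for a never-transplanted child. Section 3.3.4 mentions separate consortium work on survivorship bias, but section 6.2 takes no rule from it.

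**3. Entry.** A child aged 18 at activation (2016.17) could not have joined the LS before age 18 − (2016.17 − 2006.0) = 7.8 years, or 8.8 years if enrolment opened at the end of 2006. This is the extreme case; a child born after opening could enter near birth.

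**4. Why the hazard shape matters.** Assume 28% mortality by 216 months (the plan gives no horizon) and a Weibull hazard with shape k. Take 11.7 months as the median surgery age. Mortality by then is 1 − exp[−0.3285 × (11.7/216)^k], where 0.3285 = −ln(0.72):

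- k = 1.0: 1.8%, or 6% of all deaths by 18 years
- k = 0.5: 7.4%, or 26%
- k = 0.3: 12.8%, or 46%

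**5. Simulation with true HR = 1.** Further assumptions: log-normal surgery age, log-SD 1.3, clipped to 1.5-186 months; half of children from the LS; follow-up to age 18; one fully measured severity covariate; 20 strata of a fitted CBPS; 400,000 children per cell. Late LS entry is uniform over 0-18 years.

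| Analysis and entry pattern | k = 1.0 | k = 0.5 | k = 0.3 |
|---|---|---|---|
| Fixed group, clock from birth; (a) all followed from birth | 0.74 | 0.49 | 0.33 |
| Same; (c) LS enters late, SPLIT captured at surgery | 1.34 | 1.45 | 1.52 |
| Same; (d) LS enters late, SPLIT recruited alive after surgery | 0.87 | 0.82 | 0.79 |
| Clock from transplant or registry entry, age at index in CBPS; (c) | 0.75 | 0.69 | 0.63 |
| Same clock; (d) | 0.49 | 0.39 | 0.34 |

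Time-dependent transplant with entry at the death-capture date gave 0.99-1.02.

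**6. Sensitivity, fixed groups.**

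- With 32-55% transplant candidates and log-SD 0.7-1.3: 0.36-0.89 (a), 1.31-1.69 (c), 0.82-0.96 (d).
- With entry built from the 2006 and 2016 dates, LS children born after opening entering at birth: 0.42-0.84 with SPLIT captured at surgery, so pattern (c) reverses direction; 0.22-0.46 with SPLIT recruited alive.
- With a true HR of 1.81: 0.69-1.42 (a), 2.43-2.87 (c), 1.48-1.63 (d); the time-dependent analysis gave 1.80-1.82.

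**7. Limits of the remedy.** If children recruited alive are entered at their surgery date, the time-dependent model fails in (d): 0.60-0.71. If crises raise the hazards of both transplant and death (by exp(0.2) to exp(0.4) each), adjusting for baseline severity alone gave 1.09-1.34, against 0.96 with no crisis effect.

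**The case against.** The plan does mention an index date, and an analyst could take it as the origin and balance on it through the score. But it is listed only as a covariate, it has no rule for controls, and in the illustration balancing age at index did not remove the bias when registry entry served as the control index. The intent-to-treat statement in section 5.6 concerns data kept after discontinuation and sets no origin. It does bear on a control who is later transplanted, so any fix must be reconciled with it.

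The stronger objection is to the sizes, and it stands. The entry ages, the spread of surgery age, the 18-year horizon and the hazard shapes are all assumed. Pattern (c) changes direction under the documents' dates. The base log-SD of 1.3 is the top of the range tried, which lengthens pre-transplant time. The mildest result, 0.96, is only 7% of the 1.81 yardstick on the log scale (ln 0.96/ln 1.81 in absolute value).

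A reader might infer that the plan states a fixed treatment group, or that its result will falsely favour transplant. The documents support neither. The fixed group is the natural reading because no time-varying term appears, but it is not declared, and the direction depends on rules left open.

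**Conclusion.** The omission is certain: time zero, the index-date rule for never-transplanted children, pre-transplant time and delayed entry are all unspecified. With treatment as a fixed group, the comparison is exposed to immortal-time bias favouring transplant and to left-truncation bias in either direction by source, and CBPS removes neither. Analysts following section 6.2 could reach opposite conclusions from the same data.

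The size and net direction are not settled. The fixed-group range of about 0.2 to 1.7 at a true HR of 1 shows what is possible under the stated assumptions; it is not a forecast. It leaves out unmeasured severity, which matters because Table 2 shows median peak ammonia of 958 in transplanted against 403 in conservatively managed children. The rules need to be fixed before outcomes are examined.

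**What to change.** In section 6.2:

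1. State the time scale and time zero.
2. Fit the Cox model in counting-process form on the age scale, with transplant as a time-dependent covariate. Count time from entry to surgery as conservative.
3. Set entry by source as the date from which a death would have been captured: LS enrolment; the SPLIT record date if registry data are merged; actual study enrolment, not the surgery date, for children recruited alive through SPLIT or NUCDF.
4. Use only covariate values measured before transplant or, for controls, before the matched or index age. State how changing covariates (prior hyperammonemic events, clinic ammonia) enter the score, for example by CBPS matching within risk sets at the age of transplant.
5. Use a landmark or risk-set-matched version for the Kaplan-Meier and log-rank step.
6. Reconcile this with section 5.6 by stating how a control who is later transplanted is analysed.

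The cost is wording, programming, and the source plus three dates per child: entry, transplant, and death or last contact. Section 4.5 promises care with historical dates but does not list these, so their availability in each source must be confirmed. Some person-time is lost. In simulated samples of 185 the standard error of the log HR rose by 0.3-2.4%; it would rise more if a source holds deaths from before its capture date.

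### If the treatment effect on survival varies with CBPS, section 6.2 stratifies the Cox model, which usually still gives one common hazard ratio; the treatment-by-CBPS term promised earlier in 6.2 is not named for survival

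*Combined protocol and SAP*

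**What the plan says.** All of this is in section 6.2, Analysis Plan, under Aim 1.

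- **Screening.** Before any model is fitted, "we will compare survival times based on the log-rank test in Kaplan-Meier analysis", and mean scores by t-test, in each case "within each stratum to evaluate evidence of heterogeneity". The strata are formed by cutting the CBPS.
- **What heterogeneity means.** "Evidence of heterogeneity will provide clues to interactive effects based on UCD severity". In other words, the treatment effect may change with CBPS, which the plan treats as a marker of severity.
- **General response.** These effects "will be modeled in regression analyses below by including a cross products term of treatment type with CBPS".
- **Neurodevelopment and quality of life.** Each model holds treatment and the baseline measurement, "as well as the CBPS and if necessary the cross product of treatment type by CBPS".
- **Survival.** The Cox model "will either control for CBPS or stratify on it in the case of heterogeneity". This sentence names no product term and promises no hazard ratios by stratum or by CBPS level.

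**The concern.** The trigger is effect modification: transplantation compares differently with conservative management at different CBPS values. Stratifying a Cox model answers another problem, baseline hazards that differ in shape or level between strata. It leaves a single treatment coefficient. An analyst who follows the survival sentence literally would see heterogeneity in the stratum comparisons, stratify, and then report one hazard ratio that assumes the heterogeneity is absent.

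Survival is the first outcome named in Aim 1 (section 2), and section 3.3.4 asks for a survival comparison that takes account of disorder and severity. The study exists to inform families' choice. A blended hazard ratio may describe no group of children well, and if effects run in opposite directions it could sit near 1.

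**Working it through.** **1. The two models.** With treatment x (1 = transplant) and CBPS stratum s:

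- Stratified Cox: h(t | x, s) = h0s(t) · exp(βx). The baseline h0s is free by stratum; the hazard ratio exp(β) is the same in all strata.
- With the product: h(t | x, s, c) = h0s(t) · exp(βx + γc + δ·x·c), where c is centred CBPS. The hazard ratio exp(β + δc) can now vary with CBPS.

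Only δ addresses what the screening step looks for.

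**2. The plan's own survival figure.** Section 6.2 gives one: 80% power for an increase of about 60% over 28% mortality (28% to 44.8%), with group sizes "of 90 and 80 in 2-tailed testing at an alpha of 0.05". It assumes a common effect and says nothing on heterogeneity. It does not reproduce (two-proportion power is 60% at 80 per group and 65% at 90), but that is a separate matter and is not used below beyond the 28% and the group sizes.

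**3. Where the common hazard ratio lands.** With equal arms within strata, the stratified estimate is roughly the average log hazard ratio weighted by expected deaths. The number of strata, the follow-up and the stratum hazard ratios are not in the plan. I assume two equal strata, a common end of follow-up, and control risk p; transplant risk is then 1 − (1 − p)^HR. Weights are control risk plus transplant risk.

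- *HR 2 and 0.5, p = 28% in both.* Weights: 0.28 + 0.4816 = 0.7616 and 0.28 + 0.1515 = 0.4315. Log HR = 0.6931 × (0.7616 − 0.4315) / 1.1931 = 0.192, so HR = 1.21.
- *HR 2 at p = 16%, HR 0.5 at p = 40%.* Weights: 0.16 + 0.2944 = 0.4544 and 0.40 + 0.2254 = 0.6254. Log HR = 0.6931 × (0.4544 − 0.6254) / 1.0798 = −0.110, so HR = 0.90.
- *HR 3 and 1/3, p = 28% in both.* Weights: 0.28 + 0.6268 = 0.9068 and 0.28 + 0.1037 = 0.3837. Log HR = 1.0986 × (0.9068 − 0.3837) / 1.2905 = 0.445, so HR = 1.56.

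The blend depends on where the deaths fall. Near-cancellation is possible, not automatic.

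**4. Simulation of the same designs** (exponential survival, 1,500 runs per row, likelihood-ratio tests at two-sided 0.05):

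| HR, stratum 1 / 2 | Control risk, 1 / 2 | Per group | Median common HR | Common HR significant | Product term significant | Within-stratum test significant, 1 / 2 |
|---|---|---|---|---|---|---|
| 2 / 0.5 | 28% / 28% | 80 | 1.19 | 10.2% | 64.0% | 48.0% / 32.9% |
| 2 / 0.5 | 28% / 28% | 90 | 1.22 | 9.6% | 66.9% | 51.2% / 30.1% |
| 2 / 0.5 | 16% / 40% | 80 | 0.89 | 6.9% | 58.0% | 30.5% / 41.6% |
| 2 / 0.5 | 16% / 40% | 90 | 0.90 | 6.3% | 65.9% | 33.9% / 43.5% |
| 3 / 0.33 | 28% / 28% | 80 | 1.56 | 33.8% | 93.1% | 89.8% / 54.5% |
| 3 / 0.33 | 28% / 28% | 90 | 1.54 | 37.1% | 95.1% | 93.3% / 57.8% |
| 1 / 0.5 | 16% / 40% | 80 | 0.62 | 29.2% | 16.7% | 5.8% / 37.8% |
| 1 / 0.5 | 16% / 40% | 90 | 0.64 | 30.9% | 19.4% | 4.8% / 43.1% |

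The last two rows show that effects need not oppose each other for the single figure to mislead: 0.62 to 0.64 fits neither 1 nor 0.5. With a true common HR of 1.6 (800 runs at each group size) the product test rejects in 4.9% of runs, as it should.

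**5. Five smaller strata.** Assumed: 180 children, 18 per arm in each stratum, baseline hazards 0.02 to 0.08 per year, censoring uniform on 3 to 13 years, about 51 to 55 deaths. With HRs running from 2.0 to 0.5 across strata, repeated simulations (200 to 500 runs) gave a common HR of 0.92, significant in 5 to 6% of runs; the product term was significant in 36 to 40%. With HRs from 2.5 to 0.4 it was significant in about 60%. For 2.0 to 0.5, the within-stratum tests at the two ends were significant in 16% and 23%. With no effect anywhere, at least one of the five was significant in about 20% of runs (independent tests would give 1 − 0.95^5 = 23%).

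**The case against.** Four points deserve weight.

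1. *The general rule may already cover survival.* The product term is promised for the regression analyses that follow, survival is among the outcomes screened just before, and the Cox model is one of those analyses. This is a fair reading. But the later sentence is the specific instruction for survival and puts stratification where the other outcomes get the product. At best 6.2 is unclear.

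2. *Opposite effects would be visible beforehand.* Kaplan-Meier curves within strata could show them, and the stratified fit is used only once heterogeneity has been noticed. This stands against any claim that the effects would be hidden. It does not repair the model: those comparisons come before it, give no adjusted estimate, and have little power in small strata.

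3. *Stratify may mean separate Cox models by stratum.* That would give stratum-specific hazard ratios and remove the defect. The text neither says so nor excludes it.

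4. *The scenarios are chosen.* Hazard ratios symmetric about 1 tend to cancel, and nothing in the documents points to opposite effects. CBPS is a propensity for transplantation, so its strata only approximate mild and severe disease, although 6.2 makes that link itself. All of this stands.

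**Conclusion.** The point holds as a mismatch and an unclear instruction. In its usual meaning, the response named for survival does not address the heterogeneity that triggers it, and the product term promised earlier in 6.2 is not carried into the survival sentence.

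A reader might go further and infer that the plan will average opposite effects into a false finding of no difference. The documents do not support that. The general rule can be read to include the Cox model, within-stratum curves are planned, stratify can mean separate models, and cancellation needs opposing effects of roughly balanced weight, for which there is no evidence; HRs of 3 and 1/3 gave a common value of about 1.55.

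On size: for assumed HRs of 2 versus 0.5, the common hazard ratio lies between 0.89 and 1.22 and is significant in about 5 to 10% of runs, against 36 to 67% for the product term, depending on the design. The algebra in step 1 needs no assumptions; every percentage rests on assumed strata, hazards and follow-up. The change is worth making, but it does not threaten the study.

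**What to change.** Replace the survival sentence in 6.2 with wording such as: *In the case of heterogeneity, the Cox model will include treatment, centred CBPS and the treatment-by-CBPS product. If baseline hazards also differ, the model will in addition be stratified on CBPS strata. Hazard ratios with 95% confidence intervals will be reported at low, middle and high CBPS, at values fixed in advance.* If separate models by stratum are what is meant, say so and commit to reporting each hazard ratio.

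The cost is one sentence, one model term and one degree of freedom, with wider intervals for CBPS-specific hazard ratios than for a single common one. Power for the product is modest (about 36 to 67% for HRs of 2 versus 0.5, and 17 to 19% for 1 versus 0.5, under the assumptions above). The plan should therefore add that a non-significant product is not evidence of a uniform effect; the estimates and intervals across CBPS are the useful output.
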